14.2 Phase II

14.2.1 Primary endpoint

14.2.1.1 For Group 1 (relapsed or refractory NB)

The objective is to improve overall response rate (ORR) defined as the proportion of patients achieving CR or PR based on revised INRC as the best response at the end of cycle 2 and cycle 4. The phase II study of ch14.18 + GM-CSF for relapsed/refractory NB (POG 9347) demonstrated overall response rate of 17. 8% in a total 28 patients.⁹⁴ Our phase II study of 3F8 + GM-CSF for refractory NB had ORR of 28.8% (13 CR+PR out of total 45).⁹⁵ Based on these clinical trial results we decided that the historical ORR of refractory/relapsed NB by antibody therapy is < 25 %.

Our null hypothesis is that the hu3F8-BsAb treatment has ORR < 25%. The alternative hypothesis is that the ORR after the hu3F8-BsAb treatment is 50%.

We will accrue 30 patients. At the end of the trial 95% one-sided confidence interval for ORR will be computed using Wilson's method. If the confidence interval does not include the null ORR rate of 25% we will consider this treatment successful. The sample size is based on confidence interval half-width

0.15 and desirable ORR rate of 50%. Based on simulation if the true rate is 50% the CI will not include 25% with probability 90%.

Patients who received at least 1 dose of hu3F8-BsAb will be included into the assessment even if they are removed from the study before completing cycle 4 due to any reasons. We expect to enroll 10-15 patients/year, therefore accrual of this group will be completed in 2-3 years.

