2.1.2. Phase II

After RP2D is determined, a phase II trial will be carried out to assess the anti-tumor activity of hu3F8-BsAb. Two groups of patients will be studied: Group 1 will consist of patients with relapsed or refractory NB and Group 2 of relapsed or refractory measurable osteosarcoma. Hu3F8-BsAb is given on Days 1 and 8 of each cycle. The duration of each cycle is 28 days. However, cycles may be delayed for up to 56 days if >grade 2 toxicity is encountered.

HAHA titer will be measured after each cycle. If HAHA develops, cycles are deferred for up to 120 days until HAHA titer <1300 U/ml. Extent of Disease Evaluation (EOD) will be performed after the second dose of cycle 2 and cycle 4, then every 3 months thereafter.

A total of 4 cycles will be given, and patients with no life-threatening toxicity clearly attributable to hu3F8-BsAb, no progressive disease, continuing to meet all eligibility criteria and HAHA titer is <1300U/ml have the option of receiving additional cycles up to 2 years from the start of the Hu3F8-BsAb treatment. Patients may continue therapy beyond 4 cycles even if they achieve remission.

After cycle 4, duration between cycles can range from 28-120 days. Patients will undergo physical examination, Complete Blood Count (CBC) and complete chemistry and immune correlates will be tested as described in Protocol Section 10.

For Group 1, the overall response rate will be evaluated and is defined as the proportion of patients achieving Complete Remission (CR) or Partial Response (PR) based on revised International Neuroblastoma Response Criteria (INRC)³ as the best of the responses at the end of cycle 2 and cycle 4. (See Section 2.4.2.1) excluding potential response assessments after initiation of any new prohibited anticancer treatment).

For Group 2, 4-month Progression Free Survival (PFS) will be assessed and is defined as the proportion of patients who have not developed progressive disease nor died at the end of 4 months from the first dose of Hu3F8-BsAb. In addition, number of patients who have CR or PR as the best of the responses at the end of cycle 2 and cycle 4 will be determined. (see Section 2.5.2.2)

Hu3F8-BsAb is given IV over ~1-3 hours on Days 1 and 8 for each cycle.

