2.4.2. Phase II

2.4.2.1. ORR For Group 1 (relapsed or refractory NB)

For relapsed or refractory NB patients, the primary endpoint will be the ORR defined as the proportion of patients achieving CR or PR based on INRC as the best response at the end of cycle 4.

For this analysis, Best Overall Response (BOR) will be derived as the best response at the end of cycle 4, excluding any potential response assessments after initiation of any new prohibited anticancer treatment.

Overall response will be defined by the investigator in the Response Summary eCRF form by combining response of the individual components (i.e. soft tissue, bone, and bone marrow disease):

- Complete Response/Remission (CR): All components meet criteria for CR.

- Partial Response/Remission (PR): PR in at least one component and all other components are either CR, Minimal Disease (MD) (bone marrow), PR (soft tissue or bone), or Not Involved (NI)*; no component with progression disease.
- Mixed Response (MR): PR or CR in at least one component but at least one other component with Stable Disease; no component with PD.
- Stable Disease: Stable Disease in one component with no better than Stable Disease or NI* in any other component; no component with progressive disease.
- Progressive Disease: Any component with Progressive Disease.
 *NI Site not involved at trial entry and remains uninvolved.

Mixed Response corresponds to Minor Response in the *Revisions to the International Neuroblastoma Response Criteria: A Consensus Statement From the National Cancer Institute*³. Thus it will be considered as Minor Response for the analyses.

Primary (soft tissue) Tumor Response:

- CR: <10mm residual soft tissue at primary site AND Complete resolution of MIBG or Fluorine-18-Fluorodeoxyglucose Positron Emission Tomography (FDG-PET) uptake (for MIBG-nonavid tumors) at primary site.
- PR: ≥30% decrease in longest diameter of primary site AND MIBG or FDG-PET uptake at primary site stable, improved, or resolved.
- Progressive Disease: >20% increase in longest diameter taking as reference the smallest sum on trial (this includes the baseline sum if that is the smallest on trial) AND Minimum absolute increase of 5mm in longest dimension.
- Stable Disease: Neither sufficient shrinkage for PR or sufficient increase for PD at the primary site.

Tumor Response at Metastatic Soft Tissue and Bone Sites:

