2.6.2.3. Stool Microbiome

Based on emerging data on the impact of stool microbiome on function of immunotherapeutic agents, a stool sample will be collected on all patients prior to first dose of hu3F8-BsAb, where feasible.

2.6.2.4. Disease Control Rate (DCR) at Cycle 4

DCR is defined as :

- patients whose BOR at cycle 4 is CR, PR, MR or Stable Disease using INRC
- patients whose BOR at cycle 4 is CR, PR or Stable Disease, using RECIST v1.1.

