6.6.1. Primary Efficacy Analysis for Phase II

6.6.1.1. ORR for Group 1

The primary efficacy variable of relapsed or refractory NB patients of phase II is defined as ORR at the end of cycle 4 excluding potential response assessments after initiation of any new prohibited anticancer treatment.

The null hypothesis is that the hu3F8-BsAb treatment has ORR < 25%. The alternative hypothesis is that the ORR after the hu3F8-BsAb treatment is \geq 25%.

90% and 95% two-sided confidence intervals for ORR will be computed using Wilson's method. If the two-sided 90% confidence interval does not include the null ORR rate of 25% the treatment will be considered as successful.

Patients in the FAS will be included into the assessment even if they are removed from the trial before completing cycle 4 due to any reasons.

The number and percentage of responder patients (Yes/ No) with details by best response categories (CR, PR and MR versus Stable Disease, Progressive Disease, Not Evaluable, Missing) will be described in the FAS and the confidence interval using the Wilson's method will be provided.

In addition, overall responses at each cycle will excluding potential response assessments after initiation of any new prohibited anticancer treatment be provided with the 90% and 95% confidence intervals using the Wilson's method.

Patients whose CRF response is "Very Good Partial Response" will be considered as "Partial Response" for the analyses.

ORR values will be also presented in a data listing as well as overall responses at each cycle.

6.6.1.2. 4-month PFS for Group 2

The primary efficacy variable of relapsed or refractory osteosarcoma patients of phase II is defined as 4-month PFS.

The null hypothesis is that the hu3F8-BsAb treatment has 4-month PFS <12%. The alternative

hypothesis is that the 4-month PFS after hu3F8-BsAb treatment is $\geq 12\%$.

The Kaplan-Meier estimate of the median time will be provided with 25th percentile and 75th percentile as well as PFS rates at 4 months with corresponding 90% and 95% Confidence Intervals.

In addition, the results will be presented graphically in Kaplan-Meier plots including count for numbers of patients at risk.

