6.8.2. Presentation of PK Data

If the actual time of sample collection deviates from the nominal time by more than $\pm 10\%$, the serum concentration will be flagged and may excluded from the summary statistics.

Individual concentrations deemed to be anomalous will be flagged in the listings and excluded from the summary statistics.

For PK parameters the following rule will apply:

Geometric mean and coefficient of variation will not be calculated for t_{max}.

Summary tables, arithmetic mean (+ standard deviation [SD]) figures, overlaying individual figures, and individual figures by treatment and time postdose will be provided for serum PK concentrations in the intensive PK sampling period of Phase 1. All figures will be produced on both linear-linear and linear-logarithmic scales. The +SD bars will only be displayed on the linear-linear scale. Summary tables by treatment will be provided for all PK parameters, with the exception of diagnostic regression-related PK parameters.

For sparse PK sampling in Phase 1 and 2 (prior to and \sim 5 minutes after hu3F8-BsAb infusion), serum concentrations will be listed and summarized by phase, cycle and timepoint.

7. Changes in the Conduct of the Trial or Planned Analysis

The changes indicated below are being made before any data analysis and correspond to changes to protocol version 8. None of these changes are documented as formal protocol amendments:

- MTD is not exactly defined as a maximum dose level at which ≤ 1 of 6 patients experiencing DLT but it is defined as the dose level that leads to DLT in approximately 15% of patients (posterior probability of DLT that comes closest to the toxicity level of 0.15). This has been clarified.
- A DLT Evaluable Analysis Set (defined as all patients in the dose escalation phase who receive both doses of hu3F8-BsAb in cycle 1 and had sufficient safety evaluations, or who had a DLT during the DLT evaluation period) will be considered to evaluate the toxicity instead of "all enrolled patients who received their assigned dose"
- For PFS and OS definition, first dose of treatment will be considered instead of enrollment date as defined by Tinazzi¹⁰
- Death is considered for PFS definition to be consistent with Tinazzi¹¹
- CR duration will be calculated from the time of remission (which is consistent with the definition in the statistical section of the protocol) instead of from first day of treatment (mentioned in the efficacy section of the protocol)

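### SAP 6.6.1.1 counts Mixed Response as response in the Group 1 primary analysis, although the endpoint is CR or PR only; if followed, one patient can turn a failure into a success

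*SAP*

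**What the plan says.** **Endpoint definition.** SAP 2.4.2.1 gives the Group 1 primary endpoint as "ORR defined as the proportion of patients achieving CR or PR based on INRC as the best response at the end of cycle 4". SAP 2.1.2 agrees: "the overall response rate will be evaluated and is defined as the proportion of patients achieving Complete Remission (CR) or Partial Response (PR", followed by the reference to the revised INRC. Protocol 4.1.2 and 14.2.1.1 use the same two categories.

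**Mixed Response.** SAP 2.4.2.1 defines MR as a category of its own: CR or PR in at least one component, at least one other component only stable, and none progressing. It equates MR with the INRC category of minor response: "Thus it will be considered as Minor Response for the analyses". The one endpoint that expressly counts MR is the exploratory disease control rate in SAP 2.6.2.4: "patients whose BOR at cycle 4 is CR, PR, MR or Stable Disease using INRC".

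**Primary analysis.** SAP 6.6.1.1 declares success if the two-sided 90% Wilson interval for ORR excludes 25%. It then asks for the number and percentage of responders (Yes/No), with best response shown as "CR, PR and MR versus Stable Disease, Progressive Disease, Not Evaluable, Missing". The sentence ends by saying that these "will be described in the FAS and the confidence interval using the Wilson's method will be provided".

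**Declared changes.** SAP section 7 opens with "The changes indicated below are being made before any data analysis and correspond to changes to protocol version 8". Its list covers the MTD definition, the DLT set, the PFS method, the HAHA analysis and other items. Adding MR to the ORR is not among them.

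**The concern.** The SAP offers two numerators for one primary endpoint, and the one in the analysis section contradicts the definition. SAP 6.6.1.1 does not restate that ORR means CR or PR, so the split is its only description of who counts as a responder.

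The matching Group 2 sentence in SAP 6.6.3.5 has the same structure, with CR and PR before the word versus and everything else after it. This shows that the left side is the responder side. RECIST has no MR category, so MR was added for Group 1 and put on the left.

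The 25% null rests on historical response rates. For one of the two studies, protocol 14.2.1.1 shows the count: "ORR of 28.8% (13 CR+PR out of total 45". Setting CR+PR+MR against that benchmark compares a wider numerator with a narrower one, always in the direction of success.

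**Working it through.** **Inputs from the documents**
- n = 30, null 25%, alternative 50%, two-sided 90% Wilson interval, stated power 90% (SAP 2.3.2.1, 6.6.1.1; protocol 14.2.1.1).
- Missing responses count as non-response (SAP 5.2.1).
- MR rate: not given. Assumed values m = 3%, 5%, 10%, 15%.

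**Step 1. Success threshold.** With p = x/n and z = 1.645, the Wilson lower limit is

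[p + z²/(2n) − z·√(p(1−p)/n + z²/(4n²))] / (1 + z²/n)

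For n = 30, z²/(2n) = 0.0451, z²/(4n²) = 0.00075 and 1 + z²/n = 1.0902.
- x = 11: (0.3667 + 0.0451 − 0.1516)/1.0902 = 0.239, below 0.25, fails.
- x = 12: (0.4000 + 0.0451 − 0.1539)/1.0902 = 0.267, above 0.25, succeeds.

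So success needs x ≥ 12.

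**Step 2. Reproduce the plan's figure.** Exact binomial, CR+PR only:
- P(X ≥ 12 | 30, 0.50) = 0.900, which matches the stated 90%.
- P(X ≥ 12 | 30, 0.25) = 0.051, the type I error.

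**Step 3. Reversals that need no MR rate**

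| Result in 30 patients | CR+PR only | Split in 6.6.1.1 |
|---|---|---|
| 11 CR/PR + 1 MR | 11/30, limit 0.239, fails | 12/30, limit 0.267, succeeds |
| 9 CR/PR + 3 MR | 9/30, limit 0.184, fails | 12/30, limit 0.267, succeeds |

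**Step 4. Probability of success.** Let p now be the true CR+PR rate. If MR is counted, the responder rate becomes p + m, so P(success) = P(X ≥ 12 | 30, p + m).

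| p | MR not counted | m = 3% | 5% | 10% | 15% |
|---|---|---|---|---|---|
| 20% | 0.0095 | 0.028 | 0.051 | 0.159 | 0.345 |
| 25% | 0.051 | 0.106 | 0.159 | 0.345 | 0.569 |

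**Step 5. Probability of opposite decisions.** Twelve or more CR+PR implies twelve or more CR+PR+MR. The two numerators therefore disagree with probability P(X ≥ 12 | p + m) − P(X ≥ 12 | p). For example, at p = 25% and m = 5%: 0.1593 − 0.0507 = 0.109.

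| p | m = 3% | 5% | 10% | 15% |
|---|---|---|---|---|
| 25% | 0.055 | 0.109 | 0.294 | 0.518 |
| 30% | 0.104 | 0.186 | 0.410 | 0.608 |
| 50% | 0.047 | 0.067 | 0.092 | 0.099 |

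**The case against.** The strongest reply is that the success rule in 6.6.1.1 is written in terms of ORR, and that ORR is defined as CR or PR throughout, including for Phase I (SAP 2.5.1.3) and Group 2 (SAP 2.5.2.2). On this reading the disputed sentence comes after the rule, describes a table, and redefines nothing. The silence of section 7 points to a drafting slip, for which the definition should govern.

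Much of this is fair. A slip is the likelier explanation, and someone working from 2.4.2.1 would obtain the right numerator. But the sentence names responders, divides them Yes/No and attaches the Wilson interval on which the decision rests. The SAP has no rule saying which section prevails. SAP 6.1 leaves table formats to shells that are outside these documents, so whether the error reaches the output cannot be checked here.

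Three narrower points also stand:
- Equating MR with minor response only relabels it; the case rests on the CR-or-PR definition.
- The largest probabilities need a 15% MR rate and a true CR+PR rate near the null. At the design alternative of 50% the two numerators disagree in at most about 10% of trials over the assumed range.
- The threshold of 12 holds for 30 analysed patients. The FAS (SAP 4.3) is everyone dosed. By the same formula, 11 responders suffice at n = 28 (lower limit 0.257) and 13 are needed at n = 32.

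**Conclusion.** The concern holds. As written, SAP 6.6.1.1 puts MR with the responders, against the endpoint definition in both documents and without a declared change. At n = 30 a single MR patient alongside 11 CR/PR patients reverses the primary conclusion, and this needs no assumption about how common MR is. At the 25% null, the false-success rate would be 0.11 to 0.57 instead of 0.051 for assumed MR rates of 3% to 15%. All these consequences are conditional on 6.6.1.1 being followed rather than 2.4.2.1. Because the choice can decide the trial's primary result, it must be settled in the SAP before responses are analysed; settling it afterwards would be a post hoc choice.

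**What to change.** In SAP 6.6.1.1, list CR and PR as the responder categories, and MR, Stable Disease, Progressive Disease, Not Evaluable and Missing as the non-responder categories. Check that the Group 1 ORR table shell uses the same split.

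As a separate clarification, state success in 6.6.1.1 and 2.3.2.1 as the lower limit of the two-sided 90% Wilson interval exceeding 25%. Read literally, the present rule is also met by an interval lying wholly below 25%, as with 3 of 30 responders (upper limit 0.226). The count of 12 of 30 may be given as an illustration; if the FAS is not exactly 30, the lower-limit rule governs.

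The cost is a wording change in the SAP and a check of one shell. Sample size is unchanged, and at n = 30 type I error stays at 0.051 and power at 0.90.

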6.6.2. Sensitivity for the Primary Analyses

For ORR analysis in group 1 of phase II, the ORR at the end of the trial excluding potential response assessments after initiation of any new prohibited anticancer medication will be also studied and the two-sided confidences intervals (90% and 95%) using the Wilson's method will be provided.

6.6.2.1. Analyses Addressing Underlying Assumptions of Models

Not applicable

6.6.2.2. Analyses Addressing the Effect of Stratification Variable(s)

Not applicable

6.6.2.3. Analyses Addressing the Effect of Intercurrent Events

Not applicable

6.6.2.4. Analyses Addressing the Effect of Missing Data

Not applicable

6.6.3. Secondary Efficacy Analysis

6.6.3.1. ORR for Phase I

ORR for patients from phase I will be estimated for each disease type (excluding potential response assessments after initiation of any new prohibited anticancer treatment) and provided

Final, Version 1.0, 06Oct2021

with 90% and 95% two-sided Confidence Intervals using Wilson's method, by treatment group in the FAS.

For NB, anti-tumor activity will be measured by revised INRC, as described in section 2.4.2.1.

For osteosarcoma and other GD2(+) tumors, the response and progression will be evaluated in this trial using the RECIST Committee, version 1.1. as described in Section 2.5.1.3. The proportion of NB, osteosarcoma, and other GD2(+) tumor patients responding to therapy will be determined for each disease type.

In addition, overall response at each cycle excluding potential response assessments after initiation of any new prohibited anticancer treatment will be provided with the two-sided 90% and 95% confidence intervals using the Wilson's method.

Swimmer plot will also be produced (split by disease type if needed) with the following characteristics:

- Responses at each cycle over time for X axis starting from the first treatment date
- Dose levels and patient numbers for the Y axis.

Patients whose CRF response is "Very Good Partial Response" will be considered as "Partial Response" for the analyses.

ORR values will be also presented in a data listing as well as overall responses at each cycle.

6.6.3.2. PFS for Phase I

PFS analyses will be performed in patients from the FAS.

The number of overall censored patients, number of patients with events and Kaplan-Meier estimates median time will be provided with 25th percentile and 75th percentile and 95% Confidence Interval.

In addition, the results will be presented graphically in Kaplan-Meier plots including count for numbers of patients at risk.

Frequency (number and percentage) of patients with an event (progression or death) and censoring reasons will be presented by treatment group. See section 2.4.2.2 for details of censoring reasons.

PFS values will be also presented in a data listing.

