14.1.2 Secondary endpoints

14.1.2.1 Pharmacokinetics of hu3F8-BsAb

PK will be measured by serial blood sampling during cycle 1 as listed in Table 5. PK analysis will be carried out by noncompartmental analysis of the serum concentration-time data. The following variables are determined: area under the serum concentration-time curve (AUC), the maximum serum concentration (C_{max}), the time to reach the maximum concentration (t_{max}), and the terminal half-life ($t_{1/2}$). The variables AUC and $C_{max(ss)}$ are dose normalized in order to calculate clearance (C_{Lss}), volume

of distribution (V_{ss}) at steady state, the accumulation index for AUC ($R_{A,AUC}$), C_{max} ($R_{A,Cmax}$), apparent terminal half-life, and mean residence time.

14.1.2.2 To assess the activity of hu3F8-BsAb against NB, osteosarcoma, and other GD2(+) tumors and to assess HAHA response

For NB, anti-tumor activity will be measured by revised INRC. For osteosarcoma and other GD2(+) tumors, the response and progression will be evaluated in this study using the Response Evaluation Criteria in Solid Tumors (RECIST) Committee, version 1.1. as described in Section 12.⁹³ The proportion of NB, osteosarcoma, and other GD2(+) tumor patients responding to therapy will be determined for each disease type. HAHA will be measured as previously described and the proportion of patients developing HAHA after hu3F8-BsAb therapy will be determined. The correlation between HAHA response and overall response (for neuroblastoma), disease control (for osteosarcoma), overall survival, and progression free survival will be assessed. The correlation between HAHA response and overall response rate (for neuroblastoma) or disease control rate (for osteosarcoma) will be tested using chi-square test. Kaplan-Meier method will be used for estimating overall survival and progression-free survival. Log-rank test will be used for assessing the correlation between HAHA response and the survivals (e.g. OS, PFS) in univariable analysis. Cox-Regression will be used for multivariable analysis for variables including known prognostic factors and HAMA response if p<0.05 in the univariable analysis. This information will be summarized separately by cancer type.

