2.1. Overall Trial Design

This is a phase I/II trial which will assess the toxicity and pharmacokinetics (PK) of the humanized anti-disialoganglioside (GD2) x anti-CD3 bispecific antibody (Hu3F8-BsAb) in phase I and the anti-tumor activity of hu3F8-BsAb in phase II.

In phase I, dosages of hu3F8-BsAb will follow a dose-finding design in order to determine the Maximum Tolerated Dose (MTD) in cohorts of patients with relapsed/refractory neuroblastoma (NB), osteosarcoma, or other GD2(+) solid tumors. The Recommended Phase II Dose (RP2D) will be established. Hu3F8-BsAb PK will be also evaluated.

In phase II, patients with relapsed/refractory NB (Group 1) and osteosarcoma (Group 2) will be treated with hu3F8-BsAb at the RP2D and anti-tumor activity will be assessed.

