4.3. Full Analysis Set

The Full Analysis Set (FAS) will consist of all patients treated with at least one dose of treatment.

The FAS will be used for summaries and analysis of demographics and baseline characteristics, treatments and medications, secondary efficacy endpoints and will be the primary analysis set for the analysis of the primary efficacy endpoints (phase II analyses).

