6.6.3.3. OS for Phase I

OS analyses will be performed in patients from the FAS.

The number of overall censored patients, number of patients with events and Kaplan-Meier estimates median time will be provided with 25th percentile and 75th percentile and 95% Confidence Interval.

In addition, the results will be presented graphically in Kaplan-Meier plots including count for numbers of patients at risk.

In addition, OS rates at different time points (every 6 months) will be estimated with corresponding 2-sided 95% CIs.

Frequency (number and percentage) of patients with an event (death) and censoring reasons will be presented by treatment group. Censoring reasons are as follows:

- Alive
- Withdrawal of consent
- Lost to follow-up

Lost to follow-up will include patients that the investigator states were lost to follow-up prior to the analysis cut-off.

OS values will be also presented in a data listing.

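### Phase I Kaplan-Meier PFS and overall survival are specified for the whole FAS with no split by tumour type, so the medians would mix case mix with drug effect

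*SAP*

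**What the plan says.** SAP 2.1 describes Phase I as enrolling "cohorts of patients with relapsed/refractory neuroblastoma (NB), osteosarcoma, or other GD2(+) solid tumors". SAP 4.3 defines the analysis set: "The Full Analysis Set (FAS) will consist of all patients treated with at least one dose of treatment".

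For Phase I PFS, SAP 6.6.3.2 states "PFS analyses will be performed in patients from the FAS". For overall survival, SAP 6.6.3.3 states "OS analyses will be performed in patients from the FAS". Both sections then list Kaplan-Meier medians, quartiles, a 95% confidence interval and plots; the survival section adds rates every 6 months. Neither names tumour type. The only grouping either mentions is for the event and censoring counts. In the PFS section it reads "censoring reasons will be presented by treatment group. See section 2.4.2.2 for details of censoring reasons". In Phase I, treatment group means the 12 dose levels of SAP Table 5.

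Protocol 14.1.2.2, whose title refers to activity against neuroblastoma, osteosarcoma and other GD2(+) tumours and to HAHA response, says "Kaplan-Meier method will be used for estimating overall survival and progression-free survival". After the HAHA log-rank and Cox sentences, the same paragraph closes with "This information will be summarized separately by cancer type".

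Elsewhere the SAP states a disease split where it wants one. For response it says "ORR for patients from phase I will be estimated for each disease type" (6.6.3.1). It also splits duration of complete remission (6.6.3.4), the Phase I HAHA models (6.6.3.6.1), Phase II overall survival (6.6.6.1) and disease control (6.6.6.6).

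**The concern.** Followed literally, 6.6.3.2 and 6.6.3.3 give one median PFS and one median survival over tumours with different natural histories. Such a median depends on how many patients of each type happened to enrol as well as on the drug. A pooled PFS curve also has no single event definition, because SAP 2.5.1.4 has progression judged by INRC for neuroblastoma and by RECIST 1.1 for the other tumours.

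Dose-level grouping cannot stand in for tumour type. With up to 30 evaluable patients over 12 levels, the average is 30/12 = 2.5 patients per level.

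At stake is how far the Phase I activity data can be interpreted. SAP 6.7.8.2 sends all Phase I efficacy analyses to the DMC with the safety and PK results, and Phase II then runs in two disease-specific groups. A pooled median says little about either disease.

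**Working it through.** **Step 1. Is a split specified anywhere for these two analyses?**

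| Analysis | SAP section | Split by disease stated? |
|---|---|---|
| Phase I ORR | 6.6.3.1 | Yes |
| Phase I PFS | 6.6.3.2 | No |
| Phase I overall survival | 6.6.3.3 | No |
| Phase II duration of CR | 6.6.3.4 | Yes |
| Phase I HAHA models for PFS and survival | 6.6.3.6.1 | Yes |
| Phase II overall survival | 6.6.6.1 | Yes |
| DCR, both phases | 6.6.6.6 | Yes |

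SAP 2.6.2 has a general statement about assessing by disease group, but it governs the exploratory endpoints listed beneath it. Phase I PFS and overall survival are secondary variables (2.5.1.4 and 2.5.1.5). Section 7, which lists changes from the protocol, does not mention the point.

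**Step 2. How much could pooling move the median?** The plan gives no figure for Phase I PFS or survival, so there is nothing to reproduce. What follows is an illustration.

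Inputs:
- Osteosarcoma 4-month PFS of 12%, from protocol 14.2.1.2 (95% CI 6% to 19%).
- 4-month PFS in the other patients: not in the documents. Assumed 40%, with 12%, 25% and 60% as the range.
- Exponential PFS in each group, an assumption. All non-osteosarcoma patients are treated as one group.

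Hazard per month: λ = −ln(S₄)/4.
- Osteosarcoma: −ln(0.12)/4 = 0.530, median ln 2/0.530 = 1.31 months.
- Others at 40%: −ln(0.40)/4 = 0.229, median ln 2/0.229 = 3.03 months.

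With osteosarcoma share w, the pooled median t solves w·exp(−0.530t) + (1−w)·exp(−λ₂t) = 0.5, where λ₂ is the hazard in the other patients.

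| Others' 4-month PFS | w = 80% | w = 50% | w = 20% |
|---|---|---|---|
| 12% | 1.31 | 1.31 | 1.31 |
| 25% | 1.42 | 1.61 | 1.83 |
| 40% | 1.51 | 1.94 | 2.53 |
| 60% | 1.63 | 2.47 | 4.05 |

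(Pooled median PFS, months, same drug effect throughout.)

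Pooled 4-month PFS in the 40% row:
- w = 80%: 0.8×0.12 + 0.2×0.40 = 17.6%
- w = 50%: 0.5×0.12 + 0.5×0.40 = 26.0%
- w = 20%: 0.2×0.12 + 0.8×0.40 = 34.4%

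**Step 3. Compare with a real effect.** A hazard ratio of 0.7 applied to both groups divides the median by 0.7. At w = 80% and others at 40%, it moves from 1.51 to 1.51/0.7 = 2.16 months. The shift in mix alone moves it from 1.51 to 2.53. Under these assumptions a change in enrolment mix could pass for a worthwhile effect, or hide one.

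**The case against.** Several stronger readings are tempting, and the objections to them largely stand.

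*That the SAP breaches the protocol without declaring it.* The closing sentence of protocol 14.1.2.2 directly follows the HAHA analyses. SAP 6.6.3.6.1 carries it over almost word for word at the end of its own HAHA section and runs those models by cancer type. The protocol paragraph also has a separate sentence giving response by disease type, which would be redundant if the closing sentence covered everything. The Phase I objectives name activity and response rates, not PFS or survival. On this narrow reading nothing was dropped and section 7 had nothing to list. The broad reading remains possible, because the Kaplan-Meier sentence is in the same paragraph, but it cannot be asserted as fact.

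*That the SAP mandates pooling.* It is silent. SAP 6.1 refers table and figure formats to shells that are not available here, and these may split by disease.

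*That the median reflects case mix instead of drug effect.* It reflects both. A disease-specific median would not isolate drug effect either: it is uncontrolled and spans 0.009 to 501.3 mcg/kg/cycle, with escalation within patients allowed after cycle 2.

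*That pooling is what prevents comparison with the 12% benchmark.* SAP 6.6.3.2 plans no tabulated 4-month rate, so splitting alone would not supply one. The protocol uses 12% only for Phase II Group 2, which has its own analysis.

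*That the RP2D choice is at risk.* The stated basis is safety, or PK if no MTD or DLT is found. The DMC does see Phase I efficacy, but no PFS or survival criterion is given.

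Disease-specific ORR, DCR and patient-level listings are planned as well. None of this supplies the missing Kaplan-Meier split.

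**Conclusion.** The point holds as a minor improvement. SAP 6.6.3.2 and 6.6.3.3 specify Phase I Kaplan-Meier analyses in all treated patients with no tumour split, out of line with how the SAP handles Phase I response and disease control. The protocol supports a split on one reasonable reading but does not settle it, so this is an omission to repair and not a proven departure.

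The size rests on figures that the documents do not give. There is no distortion if prognosis is equal across tumours. With the documented 12% for osteosarcoma and an assumed 40% for the rest, and exponential PFS, the pooled median runs from about 1.5 to 2.5 months as the osteosarcoma share falls from 80% to 20%. The mixing of INRC and RECIST progression in one PFS curve applies whatever those figures are. No success rule depends on these analyses.

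**What to change.** In SAP 6.6.3.2 and 6.6.3.3, state that the Kaplan-Meier estimates, plots, and event and censoring counts are given separately for neuroblastoma, osteosarcoma and other GD2(+) tumours, and that any pooled curve is supplementary. If Phase I osteosarcoma results are to be set against the 12% benchmark, add the 4-month PFS rate with its confidence interval for that group. Make the table shells match.

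The cost is a sentence or two per section and a by-group variable for disease type, which is already collected (SAP 6.4.2). No further patients or data are needed. The downside is imprecision: 30 patients in three categories average 10 each, and fewer in the smallest, so some medians may not be estimable and the intervals will be wide. That is acceptable for a descriptive analysis.
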